An X-ray will be obtained at 12 months and annually thereafter to assess anatomical changes. Only radiograph images taken up to 24 months of follow-up will be transferred to the Core Imaging Laboratory for independent review. Image acquisition, transfer, and analysis procedures will be performed using validated, prospectively defined methods. All AEs that occur during the 12 month blinded study period will be recorded. In the long-term follow-up phase (12 - 60 months), only events of interest will be recorded.

After each subject completes all 12-month follow-up evaluations, only subjects will be blinded to the individual treatment allocation resulting in single-blind design following 12-month follow-up time point. Subjects from both groups will be able to request additional injections of their originally assigned treatment as frequently⁴ as needed, provided they did not experience any significant clinical concerns after previous treatment administrations and are benefiting from it, as determined by the investigator. During the long-term follow-up phase (12 - 60 months), subjects may also elect to cross over to the other treatment arm and receive additional injections of the other treatment as frequently as needed, provided they did not experience any significant clinical concerns after previous treatment administrations and are benefiting from it, as determined by the investigator. Subjects may only cross over from their originally assigned treatment group to the other treatment group one time during the study. Subjects seeking alternative invasive OA treatment in the index knee who do not wish to cross over or who have already crossed over will exit the study, and their selected treatment option will be recorded.

⁴ Please refer to Synvisc One IFU for specified clinical use requirements.

Study Duration:	Maximum study duration per subject is 62 months: 60 r	nonths from
	treatment to last follow-up, and two additional mo	onths if the
	maximum visit window time is realized.	
Inclusion Criteria:	1. Male or female at least 18 years of age at time of	f screening.
	2. Willingness and ability to comply with study proc	cedures and
	visit schedules and able to follow oral a	and written
	instructions.	
	3. A standing knee radiograph showing a K-L gra	de of 2 to 4
	and an absence of severe osteoarthritis	defined as
	advanced stage osteoarthritis, including large o	steophytes,
	chronic fractures or bone remodeling, severe	deformity or

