### 3. Subject Disposition

A subject disposition table will be created showing the number of subjects in each treatment group that completed the study, with the number of 'in window' and 'all' visits indicated. Visits occurring outside of windows are not considered to be protocol deviations, but these windows can be used for the reporting of Adverse Events and Study Terminations, as well as for patients who return for follow-up outside of the protocol assigned visit window.

Visit windows are defined in Table 2 and Table 3.

Visit	1 Month	3 Month	6 Month	12
				Month
In-Window	± 7	± 14	± 14	± 28
	Days	Days	Days	Days
Days since Injection for In-Window Visits	23-37	77-105	169-197	337-393
Days since Injection for All Visits	1-61	62-137	138-274	275-456

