#### Table 2. Visit Windows

After each subject completes all 12 month follow-up evaluations, individual treatment allocation will be unblinded. From this time-point on, only subjects will be blinded to the individual treatment allocation resulting in a single-blind design during the long-term follow-up period. Long-term follow-up assessment visits will be at the following intervals:

Visit	18	24	30	36	42	48	54	60
	Month							
In-Window	± 28	± 28	± 28	± 28	± 28	± 28	± 28	± 28
	Days							
Days since	520-	703-	885-	1068-	1250-	1433-	1616-	1798-
Injection for In-	576	759	941	1124	1306	1489	1672	1854
Window Visits								
Days since	457-	640-	822-	1005-	1188-	1370-	1553-	1736+
Injection for All	639	821	1004	1187	1369	1552	1735	
Visits								

Table 3. Long-Term Visit Windows

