# 5. Safety Endpoints

During Phase I, all Adverse Events will be collected regardless of relationship to the device. During Phase II, only AEs that are potentially related to the device/procedure will be collected.

Adverse events will be designated in MedDRA categories by a qualified reviewer that is blinded with respect to treatment assignment. Specific adverse events are expected to occur at low frequencies, and therefore no significant differences between groups are expected. Accordingly, the *a priori* tests planned will determine whether the overall rate of adverse events differs between treatment groups, and whether differences between groups exist with respect to device relatedness and severity. Results for each category will be tabulated by treatment group. In this tabulation the number of subjects with one or more adverse events fitting into an individual adverse event (AE) category will be displayed beside the count of subjects with no AEs fitting into that category. A Fisher's Exact test will be performed to determine whether treatment groups differ. In addition, the number of AEs and the corresponding percentage of total AEs within each category of severity and relatedness to the device will be summarized by treatment. A listing of all AEs will be provided, and a narrative of each serious AE will be generated.

In addition, a time-course distribution of adverse events will be created based on contiguous intervals between planned visits, as shown in *Table 11*, *Table 12*, *Table 13*, and *Table 14*. In this table, one AE per subject, category, and time interval will be counted.

	Injection	1 Month	3 Month	6 Month	12 Month
Interval	Injection to Day 15	Day 16 to Day 61	Day 62 to Day 137	Day 138 to Day 274	Day 275 to Day 547
AEs					
AE Type 1					
AE Type 2					
Serious AE					
AE Type 1					
AE Type 2					
Device Related AE					
AE Type 1					
AE Type 2					

Table 11. Time Course Distribution of AEs - APS

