# 7. Data Collection Time Points

Data will be collected at the screening visit, the injection visit, and at 1, 3, 6 and 12 months following the injection. After each subject completes all 12 month follow-up evaluations (Phase I), individual treatment allocation will be unblinded to the investigators. From this time-point on, only subjects will be blinded to study treatments resulting in a single-blind design during the longterm follow-up period (Phase II). During Phase II of the study, the subject may opt to get additional injections of their originally assigned treatment, or they may opt to crossover to the other treatment group and may receive multiple injections of the crossover treatment. Subjects may only crossover one time during the study. In Phase II, follow-up visits will occur at six month intervals until five years following the initial injection.

The follow-up visits will preferably be completed during an office visit to ensure subject compliance, but this is not mandatory and follow-up visits may consist of a structured telephone interview or electronic self-report with exception of annual visits at which radiograph is to be taken. The investigative center will contact the subject to complete the Follow-up and AE forms. The subject will be asked to complete a Patient Questionnaire.

A table showing the data collected at each time interval is presented in the study protocol.

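### The 12-month column of the AE time-course tables (SAP Tables 11 and 12) runs to Day 547, past the SAP's own 12-month window and into Phase II, with no rule for events after re-injection or crossover

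*SAP*

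**What the plan says.** SAP section 5 plans a time-course display of adverse events "based on contiguous intervals between planned visits". In Tables 11 (APS) and 12 (HA) the columns end at Days 15, 61, 137 and 274, and the 12-month column covers "Day 275 to Day 547". Each subject is counted once per category and interval. Tables 13 and 14 repeat the layout for post-crossover events, with a first column headed by the second injection. A closing sentence of section 5 says that AEs and medication use are tabulated for the Phase I intervals.

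SAP section 3 assigns visits to windows. Table 2 gives the 12-month visit Days 275 to 456 (Days 337 to 393 in window). Table 3, introduced by "Long-term follow-up assessment visits will be at the following intervals", begins with the 18-month visit and gives it Days 457 to 639 (Days 520 to 576 in window). Section 3 also says that "these windows can be used for the reporting of Adverse Events and Study Terminations".

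Three things change when a subject finishes the 12-month evaluations:

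- **Capture.** SAP section 5 states that "During Phase I, all Adverse Events will be collected regardless of relationship to the device", but that "During Phase II, only AEs that are potentially related to the device/procedure will be collected". The protocol synopsis restricts long-term capture to events of interest.
- **Blinding.** SAP section 7: "After each subject completes all 12 month follow-up evaluations (Phase I), individual treatment allocation will be unblinded to the investigators".
- **Exposure.** The protocol synopsis (Study Design and Procedures) and SAP section 1.2 allow further injections of the assigned product, and "subjects may also elect to cross over to the other treatment arm" once in the long-term phase.

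**The concern.** A column labelled as the 12-month interval should hold events from the randomised, double-blind phase. Ending it at Day 547 brings in months of follow-up collected under different rules. Before the 12-month evaluation every AE is recorded. Afterwards an event is recorded only if it is judged potentially related (SAP) or of interest (protocol), at a time when investigators know the allocation. A reader could take a sparse last column as events dying away, when part of the sparseness comes from restricted collection.

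Exposure is the second issue. Tables 11 and 12 are labelled only by product, and no sentence stops a subject's contribution at a second injection or crossover. Without such a rule, a programmer following the shells could place an event that occurred after a switch under the product originally assigned. Events after a repeat injection of the same product have no separate table at all.

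**Working it through.** **Inputs.** Column bounds from SAP Tables 11 and 12; visit windows from SAP Tables 2 and 3; planned visits at 1, 3, 6, 12, 18 and 24 months; one month = 365.25/12 = 30.4375 days.

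**Step 1: recover the column bounds.** Take contiguous intervals between planned visits to mean that each column ends midway between adjacent visits.

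| Adjacent visits | Midpoint (months) | Midpoint (days) | Tables 11-12 | Table 2 |
|---|---|---|---|---|
| Injection / 1 month | 0.5 | 15.2 | 15 | not split |
| 1 / 3 months | 2 | 60.9 | 61 | 61 |
| 3 / 6 months | 4.5 | 137.0 | 137 | 137 |
| 6 / 12 months | 9 | 273.9 | 274 | 274 |
| 12 / 18 months | 15 | 456.6 | **547** | 456 |

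To within a day, the rule reproduces every bound in Tables 11 and 12 except the last, and every bound in Table 2. Day 547 does match the 12/24-month midpoint, 18 × 30.4375 = 547.9, but that skips the 18-month visit that both documents plan.

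**Step 2: size of the overrun against the SAP's own window.**

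- Column length: 547 − 275 + 1 = 273 days.
- 12-month window in Table 2: 456 − 275 + 1 = 182 days.
- Excess: 273 − 182 = 91 days (Days 457 to 547); 91/273 = 33%. Table 3 gives all of these days to the 18-month visit.
- Overlap with the 18-month in-window range: 547 − 520 + 1 = 28 days.

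**Step 3: share of the column that is Phase II.** Phase I ends for each subject at the 12-month evaluation, on day *s*. The share is (547 − *s*)/273.

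| 12-month evaluation on | Days after it | Share of column |
|---|---|---|
| Day 337 (earliest in window) | 210 | 77% |
| Day 365 (nominal) | 182 | 67% |
| Day 393 (latest in window) | 154 | 56% |
| Day 456 (last day of Table 2 window) | 91 | 33% |

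**Step 4: set the statements side by side.** Four statements in the SAP point to an end at or before Day 456: the Table 2 window, the Table 3 window, the between-visits rule, and the restriction to Phase I intervals. Only the column label gives Day 547.

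**Tables 13 and 14.** These also show Day 547. If their days are counted from the second injection, as the first column head suggests, their last column does not straddle the Phase I/II boundary, so the point is confined to Tables 11 and 12.

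**The case against.** The strongest reply is the closing sentence of section 5. If the tabulation covers Phase I only, Day 547 may be a loose outer limit that no Phase I event would reach, not an instruction to pool Phase II events. That is a fair reading of intent, and it means pooling is not certain. It does not settle the matter: the shells carry explicit day ranges, section 5 describes Phase II collection just before them, and nothing says which statement governs.

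Several stronger readings are tempting, and the documents do not support them:

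- **Crossover events will be counted twice or credited to the wrong product.** No text says so. The existence of Tables 13 and 14 suggests that such events are meant to be shown there. What can be said is that no censoring rule prevents it, and that same-product re-injections have no table of their own.
- **The AE rate is understated.** Tables 11 and 12 count subjects by category and interval; no person-time rate is planned. Lengthening a column can only keep or add counts. Understatement arises only if a reader divides by the interval length.
- **The APS versus HA safety comparison is contaminated.** The planned comparison is a subject-level Fisher's Exact test, described separately. No test is attached to the time-course tables, both arms use the same columns, and the column bounds do not define the period of that test.
- **Two thirds of the column is Phase II.** The 67% holds only for a 12-month evaluation on Day 365.

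**Conclusion.** The point stands as an internal contradiction with a practical consequence for a descriptive safety display. The 12-month column of Tables 11 and 12 cannot be reconciled with Table 2, Table 3, the stated basis of the intervals and the Phase I scope sentence. Followed as printed, it pools complete Phase I capture with restricted capture by unblinded investigators, after re-injection and crossover have become possible.

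The overrun is 91 of 273 days (33%) against the SAP's widest 12-month window, and 56% to 77% of the column for subjects seen in window. These are shares of calendar time. The documents give no basis for estimating how many events fall there, or how many subjects will be re-injected or cross over before Day 547. The percentages assume that days in Tables 11 and 12 run from the first injection, as in Table 2, and that Phase I ends at each subject's own 12-month evaluation, as SAP section 7 says.

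The formal AE test and the primary and secondary efficacy analyses are not shown to be affected.

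**What to change.** 1. In Tables 11 and 12, end the 12-month column at each subject's 12-month evaluation, and at latest on Day 456, so that it agrees with Table 2.
2. State in section 5 that events after any subsequent injection or crossover are excluded from Tables 11 and 12.
3. Tabulate Phase II events separately and label them as restricted capture: Tables 13 and 14 for crossovers, plus a table for subjects re-injected with the same product or given no further injection. State the day origin used in each.
4. Align the SAP and protocol descriptions of which AEs are captured after month 12, so that the Phase II tables can be labelled correctly.

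The cost is revised table shells and a few sentences of SAP text. The column correction needs no new data, no change in sample size and no change to any planned test.

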# Table 12 - Time Course Distribution of AEs - HA

	Injection	1 Month	3 Month	6 Month	12 Month
Interval	Injection to Day 15	Day 16 to Day 61	Day 62 to Day 137	Day 138 to Day 274	Day 275 to Day 547
AEs					
AE Type 1					
AE Type 2					
Serious AE					
AE Type 1					

AE Type 2			
Device Related AE			
AE Type 1			
AE Type 2			

### Table 13 - Time Course Distribution of AEs – Post-Crossover APS to HA

	2 nd Injection	1 Month	3 Month	6 Month	12 Month
Interval	Injection to Day 15	Day 16 to Day 61	Day 62 to Day 137	Day 138 to Day 274	Day 275 to Day 547
AEs					
AE Type 1					
AE Type 2					
Serious AE					
AE Type 1					
AE Type 2					
Device Related AE					
AE Type 1					
AE Type 2					

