# 1.2 Study Design

The study is a two-phase, randomized, double-blind study with a planned enrollment of 246 subjects assigned to treatment groups on a 1:1 basis. It is designed to determine whether APS provides a more effective treatment for knee osteoarthritis than HA. The study will be conducted in two phases. Phase I is the randomized, double-blind portion of the study. After each subject completes all 12 month follow-up evaluations, only subjects will be blinded to the individual treatment allocation resulting in single-blind design following 12-month follow-up time point. Subjects from both groups will be able to request additional injections of their originally assigned treatment as frequently as needed, provided they did not experience any significant clinical concerns after previous treatment administrations and are benefiting from it, as determined by the investigator. During the long-term follow-up phase (12 -60 months), subjects may also elect to cross over to the other treatment arm and receive additional injections of the other treatment as frequently as needed, provided they did not experience any significant clinical concerns after previous treatment administrations and are benefiting from it, as determined by the investigator. Subjects may only cross over from their originally assigned treatment group to the other treatment group one time during the study.

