# Table 8 - Planned Phase II Statistical Analysis – Treatment/Crossover Group

Predictor Variable	Outcome Variable(s)	Statistic	Expected Outcome
Treatment / Crossover Group	Progression to other invasive OA treatment	Chi-Square	Trend APS Superior

Treatment / Crossover Group	OMERACT-ORSI Responder / Non- Responder	Chi-Square	Trend APS Superior
Treatment / Crossover Group	WOMAC Pain, 6 Mo Intervals	One-Way Anova	Trend APS Superior
Treatment / Crossover Group	WOMAC Function, 6 Mo Intervals	One-Way Anova	Trend APS Superior
Treatment / Crossover Group	NRS Pain, 6 Mo Intervals	One-Way Anova	Trend APS Superior
Treatment / Crossover Group	EQ-5D Global Assessment 6 Mo Intervals	One-Way Anova	Trend APS Superior
Treatment / Cross Over Group	Patient Preference	Chi-Square	Trend APS Superior
Treatment / Cross Over Group	WOMAC Pain Δ: Baseline-12M	Summary Statistics and ANCOVA Model*	Trend APS Superior
Treatment / Cross Over Group	WOMAC Pain ∆: Baseline-6M	Summary Statistics and ANCOVA Model*	Trend APS Superior
Treatment / Cross Over Group	Percent of Subjects in each Treatment/Cross Over Category	Chi-Square	Trend APS Superior

\*Analysis of Covariance models will be used in order to determine if changes in WOMAC Pain score from Baseline to12 months (first model) or from 6 to 12 months (second model) differ according to what type of 2nd injection they chose to receive ( $\beta_3$ ), and whether this difference varies for APS and HA ( $\beta_2$  \*  $\beta_3$ ). The model will be as follows:

 $Y=\beta_0+\beta_1+\beta_2+\beta_3+\beta_2*\beta_3$ 

Where

 $\beta_0$ = Intercept

 $\beta_1$ = Baseline WOMAC Pain score

 $\beta_2$  = Treatment Group

 $\beta_3$ = 2nd Injection (None, Same, Crossover)

Y= Change in WOMAC Pain

In addition to these tests, results of the patient preference questionnaire will be tabulated by crossover group.

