# Table 14 - Time Course Distribution of AEs – Post-Crossover HA to APS

2 nd Injection	1 Month	3 Month	6 Month	12 Month

Interval	Injection to Day 15	Day 16 to Day 61	Day 62 to Day 137	Day 138 to Day 274	Day 275 to Day 547
AEs					
AE Type 1					
AE Type 2					
Serious AE					
AE Type 1					
AE Type 2					
Device Related AE					
AE Type 1					
AE Type 2					

A time-course tabulation showing rescue medication use (for index knee OA) by treatment group will also be generated. Adverse Event and Medication Use will be tabulated for all Phase I intervals.

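### SAP Tables 13-14 leave the time origin for post-crossover adverse events unclear, the day count never restarts at later injections, and no time-course table starts from a same-product re-injection

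*SAP*

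**What the plan says.** **Dosing in Phase II.** SAP section 1.2 states: "Subjects from both groups will be able to request additional injections of their originally assigned treatment as frequently as needed". It also states: "Subjects may only cross over from their originally assigned treatment group to the other treatment group one time during the study". SAP section 7 and the protocol synopsis allow multiple injections of the cross-over product. Nothing requires the cross-over to be the second injection.

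**Time-course tables.** SAP section 5 plans four. Tables 11 (APS) and 12 (HA) have a first column headed Injection. Table 13 is titled "Post-Crossover APS to HA" and Table 14 "Post-Crossover HA to APS"; the first column of both is headed "2 nd Injection". All four use the same intervals: Injection to Day 15, Day 16-61, Day 62-137, Day 138-274 and Day 275-547. A subject contributes at most one event per category and interval. After Table 14 the SAP adds: "Adverse Event and Medication Use will be tabulated for all Phase I intervals". It makes no matching statement for Phase II.

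**The SAP's own coding.** The ANCOVA note under Table 8 gives the second injection three levels: "Injection (None, Same, Crossover"). The SAP therefore recognises that a second injection need not be a cross-over.

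**Other AE outputs.** Section 5 also plans AE counts by treatment group with Fisher's exact test, summaries by severity and device relatedness, a listing of all AEs and narratives for serious AEs.

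**The concern.** All repeat dosing happens in Phase II, and Tables 13-14 are the only displays that start from an injection after the first. If their Day 0 is not the injection that preceded the event, an acute reaction can appear as a late one. Subjects re-injected with their own product have no display that starts from the re-injection.

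The question at stake is whether early post-injection reactions recur or worsen on a second or later injection. That lies within the trial's aims: the safety objective concerns reactions to knee injections, the safety endpoint follows AEs of interest through all time points, and injection frequency is a long-term objective. As planned, no summary would show it.

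**Working it through.** The plan gives no figure to reproduce. The check sets the permitted injection sequences against the tables.

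**1. Which sequences fit Tables 13-14?** Write A for APS and H for HA. With k injections and at most one switch there are 2k possible sequences: 2 never cross over, 2 cross over at the second injection, and 2(k - 2) cross over later.

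| Injections | Allowed | Never cross over | Cross over at 2nd | Cross over later |
|---|---|---|---|---|
| 2 | 4 | 2 (AA, HH) | 2 (AH, HA) | 0 |
| 3 | 6 | 2 (AAA, HHH) | 2 (AHH, HAA) | 2 (AAH, HHA) |
| 4 | 8 | 2 | 2 | 4 |

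Title and column header agree only in the fourth column. These are counts of sequence types, not of subjects; the documents do not say how often each is expected.

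**2. Where does an acute reaction land?** Take an illustrative subject with APS on day 0, APS on day 400, HA on day 600 and HA on day 800, and a reaction 5 days after each later injection (days 405, 605 and 805). Table day = event day - Day 0.

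| Reading of Table 13 | Day 405 (after APS) | Day 605 (after 1st HA) | Day 805 (after 2nd HA) |
|---|---|---|---|
| Day 0 = second injection, all later events | 405 - 400 = 5; APS event in an APS-to-HA table | 605 - 400 = 205; 6 Month | 805 - 400 = 405; 12 Month |
| Day 0 = second injection, post-crossover events only | not in table | 205; 6 Month | 405; 12 Month |
| Day 0 = cross-over injection | not in table | 605 - 600 = 5; correct | 805 - 600 = 205; 6 Month |
| Only subjects whose second injection was the cross-over | subject excluded | subject excluded | subject excluded |

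On the last reading, an APS-HA-HA subject with HA on days 600 and 800 is included, and a reaction on day 805 again sits at 805 - 600 = 205. So no reading puts a reaction to a repeat cross-over injection in the first column, where it belongs.

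**3. Recurrence.** The last interval spans 547 - 275 + 1 = 273 days. If two later injections are each followed by the same kind of reaction within that span, the counting rule records one event, so the recurrence is lost.

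**4. Same-product re-injection.** If Tables 11-12 count from the first injection, the day-405 reaction to the second APS injection falls in their 12 Month column. Their coverage is:
- Day 547 is 547 - 365 = 182 days past month 12, so early Phase II events enter that column, timed from the first injection.
- 60 months is about 60 x 365.25/12 = 1826 days. For subjects who never cross over, 1826 - 547 = 1279 days lie in no time-course table. That is 1279/1826 = 70% of follow-up, or 1279/(1826 - 365) = 88% of Phase II.
- A subject re-injected at month 24 (about day 730) and never crossed over is past Day 547, so no time-course column holds the resulting events.

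**The case against.** The strongest replies are these.

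- **The title governs.** An event after a second APS injection and before any HA is not post-crossover, so the title of Table 13 excludes it. The header may simply be loose wording for the cross-over injection. This stands as far as product is concerned: a reader might infer that the tables attach events to the wrong product, but that needs the header to override the title, and the SAP does not say so. In the example, both reactions after HA sit in the APS-to-HA table under every reading that includes the subject; they are mistimed, not misattributed. The reply does not rescue timing, because no restart is stated.
- **The events are reported elsewhere.** A reader might infer that events after same-product re-injection go unreported. They do not: the by-group AE tables, the severity and relatedness summaries and the full listing are not restricted to first injections or crossed-over subjects, and Tables 11-12 reach Day 547. What is missing is timing from the re-injection. Those by-group tables use the intent-to-treat set, and no rule attributes an event to the product last injected.
- **The stakes are modest.** The safety endpoint is occurrence of AEs, not their time course, and the long-term endpoints are exploratory. Re-injection depends on the investigator's judgement of benefit and of no clinical concern after earlier injections, so re-injected subjects are selected. This stands: any comparison of first with repeat injections can only be descriptive.

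**Conclusion.** The point holds for the time-course displays. Three things follow from the text:

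1. The title and time origin of Tables 13-14 conflict whenever the cross-over is the third or a later injection. Events can then be mistimed and, on a literal reading only, an event after a same-product injection can enter a cross-over table.
2. Under any reading, reactions soon after a repeat injection can be shown as late events, because the day count does not restart.
3. No time-course table starts from a same-product re-injection. For subjects who never cross over, nothing after Day 547 appears in one.

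The day-405, 605 and 805 example is illustrative, and the figures for Tables 11-12 assume counting from the first injection, since the header says only Injection. How many subjects are affected depends on re-injection rates that the documents do not give. The blinded 12-month comparison of AE occurrence is not affected, because repeat dosing starts only after it. This is a defect in descriptive Phase II reporting that should be corrected before those tables are produced.

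**What to change.** - In Tables 13-14, replace the column header and define Day 0 as the first injection of the cross-over product.
- Place each Phase II AE by days since, and product of, the most recent injection.
- Add two descriptive time-course tables for same-product re-injection (APS to APS, HA to HA).
- End follow-up in Tables 11-12 at the first subsequent injection.
- In the repeat-dose tables, apply the one-event counting rule per injection rather than per subject, with the number of injections as denominator.
- Limit any comparison with first-injection data to device- or procedure-related AEs, the only class that SAP section 5 collects in Phase II, and label it descriptive.

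The cost is SAP wording and two more tables. No new data should be needed: the Kaplan-Meier analysis in SAP Table 7 uses the date of the first subsequent injection, the protocol's long-term endpoint covers time to subsequent injections in the plural, and Tables 11-14 already need AE dates.
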